7. STATISTICAL ANALYSIS AND METHODOLOGY

The statistical analysis of the data of this protocol will be performed using SAS[®] version 9.4 or higher.

Unless otherwise specified, continuous endpoints will be summarized with number of nonmissing observations (n), mean, standard deviation (SD), median, 25^{th} quartile (Q₁) and 75^{th} quartile (Q₃), minimum and maximum. In general, the same number of decimal places as in the raw data will be presented when reporting minimum and maximum, one more decimal place than in the raw data will be presented when reporting mean and median, and two more decimal places than in the raw data will be presented when reporting SD. If the raw data have 3 decimals or more, 3 decimals will be presented for mean, median, minimum, maximum, and standard deviation.

Categorical endpoints will be described using the number and percentage of participants in the various categories of the endpoint. One decimal will be presented for percentages. Percentages equal to 100 will be presented as 100%.

All two-sided inference tests will be performed at the 0.05 significance level and all one-sided inference tests will be performed at the 0.025 significance level.

7.1 Participant Disposition and Protocol Deviations

Participants' disposition will be described by reporting the number of randomized participants, the number and percentage of participants randomized but not treated, number and percentage of participants in each of the stratification factors, the number and percentage of participants in each analysis set by treatment group. Additionally, the number and percentage of participants who completed treatment and those who discontinued treatment early along with the reason for early treatment discontinuation as well as the number and percentage of participants who completed the study or withdrew early from the study along with the reason for early withdrawal from the study will be presented by treatment group.

Number and percentage of participants randomized by site number and investigator name will also be reported by treatment group.

Incidence of major protocol deviation will be tabulated by protocol deviation category and deviation for all participants in the Full Analysis Set.

7.2 Demographics and Baseline Disease Characteristics

Demographics characteristics listed in Section 4.1 will be summarized by treatment group for participants in the Full Analysis Set.

For baseline height, weight, and BMI, 24 hours window will be added for baseline values. To be more specific, the baseline value is defined as last non-missing value prior to first dose date + 1 day. For participants who are randomized but not dosed, baseline will be the last non-missing value prior to date of randomization.

Baseline disease characteristics listed in Section 4.1 will be summarized by treatment group for participants in the Full Analysis Set. It should be noted that:

- Co-existing medical conditions of interests include the following:
 - \circ Age at screening >60
 - \circ Obesity, which is defined BMI at screening >30 kg/m²
 - Hypertension
 - Cardiovascular disease
 - Chronic lung disease
 - Chronic kidney disease
 - Chronic liver disease
 - o Chronic immunosuppression, and
 - o Diabetes

Participants in immunocompromised will be identified during the blinded medical review of participants' baseline data.

• In calculating baseline SOFA score assume the following:

| SOFA Respiratory System | PaO ₂ /FiO ₂ | SpO ₂ |
|-------------------------|------------------------------------|--------------------------|
| Score | (mmHg) | (%) |
| 0 | > 400 | > 96 on Room Air |
| 1 | 301 - 400 | >93 and < 97 on Room Air |
| | | > 93 on 1 L/min |
| | | > 96 on 2 L/min |
| 2 | 201 - 300 | 94 – 96 on 2 L/min |

• SOFA score for respiratory system could be calculated as follows:

For participants do not have SOFA score collected at baseline, the last nonmissing SpO2 respiration score prior to the first dose will be used for the baseline value.

• For participants not admitted to ICU, assume Glasgow Coma Score of 16

| Oxygen Tank Flow Rate | FiO ₂ |
|-----------------------|------------------|
| Room Air | 0.21 |
| 1 L/min Nasal Cannula | 0.24 |
| 2 L/min Nasal Cannula | 0.28 |

• Fraction of Inspired Oxygen (SpO₂/FiO₂) can be calculated as follows:

7.3 Treatment Exposure and Compliance

Number of doses received, treatment duration (in days) and percent of treatment compliance and compliance category (<80%, 80%-120%, >120%) will be summarized by treatment group for all participants in the Full Analysis Set.

COVID-19 rescue medications will be classified according to the anatomical therapeutic chemical (ATC) codes in the World Health Organization Drug (WHODRUG) dictionary; version B3 WHO Drug DDE – March 2020. The incidence rate of each classified medication will be tabulated by treatment group for all participants in the intent-to-treat population.

Concomitant medications will be classified and tabulated in a manner similar to rescue medications.

7.4. Efficacy Analysis for Secondary Endpoint

The secondary efficacy endpoint for Part 1 of this study is the median time (in hours) from randomization to hospital discharge (where discharge is defined as a score of 1 or 2 in the WHO Ordinal Scale for Clinical Improvement).

Kaplan-Meier curves will be constructed to display time-to- hospital discharge. Participants who are lost to follow-up or ended study early prior to achieving clinical improvement will be censored at the day of the last obtained assessment of their WHO Ordinal Scale for Clinical Improvement. Participants who complete follow-up without hospital discharge will be censored at the day of their Day 60 visit. Participants who die for any reason during the study will be right-censored at Day 60 or date of death, whichever is earlier. For the analysis of this efficacy endpoint, missing scores of the WHO Ordinal Scale for Clinical Improvement will be assumed to be > 2 (*i.e.*, no hospital discharge). Median time-to-clinical improvement and corresponding 95% confidence interval will be estimated from the Kaplan-Meier curves and tabulated for each treatment group.

The Cox proportional hazard method will be used to calculate the hospital discharge rate ratio of ANA001 relative to placebo while controlling for the stratification factors, baseline WHO Ordinal Scale for Clinical Improvement, and number of co-existing conditions. Hospital discharge rate ratio is akin to a hazard ratio but for the beneficial outcome of hospital discharge.

A hospital discharge rate ratio > 1 indicates a benefit for ANA001. Treatment groups will be compared using a stratified log-rank test.

The above analyses will be produced for all participants in the Full Analysis Set and by baseline WHO Ordinal Scale for Clinical Improvement scores. Additionally, the same analysis will be produced for participants in the Per-Protocol Analysis Set and Safety Analysis Set.

If WHO Ordinal Scale are missing at baseline, 6 hours window after first dose will be added for baseline values.

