Dosing will continue until the treatment course is completed. If the participant requires mechanical ventilation or for any other reason is unable to swallow oral medication over the course of the study, ANA001 should be administered via nasogastric (NG), orogastric (OG), or percutaneous endoscopic gastrostomy (PEG) tube in accordance with the appropriate section in the study Pharmacy Manual. If the participant is discharged prior to completing the treatment course, the remaining study drug will be dispensed for at-home administration. Every effort should be made to complete the remaining study assessments for participants who are not able to complete the 7-day course of study drug.

An emergency DMC meeting will convene if 3 or more blinded participants in Part 1 or 10 or more blinded participants in Part 2 experience AEs leading to premature discontinuation of study drug.

DMC assessments: After enrollment into Part 1 is completed, the independent DMC will conduct an unblinded review of safety, tolerability, and efficacy. If safety issues are identified or no potential for benefit is seen when compared with the placebo group, the DMC may recommend that the study be terminated for safety concerns or for futility. Further discussion of the terms for termination of the study are provided in Section 6.4.2.

Upon successful completion of Part 1, the safety and efficacy of ANA001 1,000 mg PO BID for 7 consecutive days will be evaluated in a larger population of patients in Part 2.

### Part 2

Participants in Part 2 will be randomly assigned to either ANA001 or matching placebo in a 1:1 ratio according to the assignment made by the randomization and trial supply management (RTSM) system. Participants will receive ANA001 or matching placebo for 7 consecutive days (defined as 14 doses administered BID). Additionally, participants will continue to receive SOC therapy (per study site policies or guidelines).

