# 6.6.2 Discontinuation or Termination of the Study

An independent Data Monitoring Committee (DMC) will be formed and constituted according to appropriate regulatory agency guidelines. Detailed information regarding the composition of the committee and detailed procedures will be provided in a separate DMC charter. The independent DMC will review the safety, tolerability, and efficacy data of Study Part 1 and Study Part 2 as described in the DMC charter.

An emergency DMC meeting will convene if 3 or more blinded participants in Study Part 1 or 10 or more blinded participants in Study Part 2 experience AEs leading to premature discontinuation of study drug.

The Sponsor may discontinue further enrollment of the study at any time (including after unblinding of Study Part 1 study data and before enrollment of Study Part 2).

Additionally, the Sponsor may (before beginning enrollment of Study Part 2):

- Exclude a specific patient subgroup due to potential safety concerns
- Modify allowed concomitant medication due to potential safety concerns, OR
- Modify other protocol criteria due to potential safety concerns (e.g., safety laboratory monitoring or PK sampling)
- Modify the sample size and/or endpoints of Study Part 2 if Study Part 1 efficacy data suggests that such changes may be necessary to adequately power Study Part 2

The DMC may also recommend interruption of recruitment at ANY time during Study Part 1 or Study Part 2 for further analysis. The DMC may also recommend termination of the study if any one of the following are observed and not associated with the natural course of COVID-19 (based on CTCAE v5:

https://ctep.cancer.gov/protocoldevelopment/electronic\_applications/docs/CTCAE\_v5\_Quick Reference 5x7.pdf):

- Grade 4 or greater nausea, vomiting, diarrhea, or abdominal pain lasting >72 hours in participants who have received maximal medical care
- Grade 4 or greater anemia, neutropenia, or thrombocytopenia without an alternative etiology

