4.3 Safety Endpoints

The following endpoints will be used to assess the safety and tolerability of ANA001:

- Incidence of treatment-emergent adverse events, serious adverse events, adverse events leading to study treatment discontinuation and adverse events leading to death
- Incidence of treatment-emergent potentially clinically significant laboratory abnormalities, including test results in the hematology, blood chemistry, and coagulation panels
- Incidence of vital signs abnormality, including temperature (°C), systolic and diastolic blood pressure (mmHg), pulse (beats/min), and respiratory rate (breaths/min).

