6. ANALYTIC DEFINITIONS

Baseline Measurements will be the last measurement for the corresponding endpoint prior to the first dose of study drug.

Age at Baseline is the last non-missing age collected before the first dose of study drug.

Body Mass Index is calculated as (Weight in kg / (Height in meter)²). The last non-missing weight and height collected before the first dose of study treatment will be used to calculate the baseline body mass index.

Study Drug Exposure is calculated as number of days from first dose day to last. That is:

Study Drug Exposure = Last Study Drug Date – First Study Drug Date + 1.

Study Drug Compliance (%) for a participant is calculated as: 100*total number of doses taken/total number of doses the participant was supposed to have taken during the treatment period. That is, 100*total number of doses taken ÷ (8* Study Drug Exposure [in Days]).

A Treatment-Emergent Adverse Event (TEAE) is any adverse event that occurs on or after first dosing and up through Day 28.

COVID-19 Rescue Treatments that are defined as any treatment approved under NDA or Emergency Use Authorization (EUA) for COVID-19 or off label medications given as direct treatment of COVID-19.

Concomitant Medication will be defined as the medications used on/after the first dose of study drug or started before first dose of study drug and continued during the study.

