7.6.1 Adverse Events

Treatment-emergent adverse events reported during the study will be coded using a MedDRA dictionary. Incidence of treatment-emergent adverse events will be summarized by treatment group and the following:

- Preferred term
- System organ class and preferred term.

These summaries will be presented for the following subsets:

- All adverse events
- Serious adverse events
- Drug-related adverse events
- All adverse events with severity \geq Grade 3
- All adverse events leading to death
- All adverse events leading to study treatment discontinuation.

A participant with multiple occurrences of the same adverse event or a continuing adverse event will only be counted once for tables reporting adverse events by preferred term and system organ class.

For tables reporting adverse events by severity, if a participant has multiple occurrences of an adverse event with the same organ class and preferred term, the most severe event will be presented. Adverse events with missing severity will be imputed to Grade 3. Additionally, for tables reporting adverse events by relationship, if a participant has multiple occurrences of an adverse event with the same organ class and preferred term, only the strongest relationship level will be presented in the relationship summary. Adverse events with missing relationship will be imputed as drug-related. Details on the treatment of missing data are provided in Section 11.2.

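### SAP 7.4 censors deaths before discharge at the date of death, so the Part 1 discharge curve, median and rate ratio are unlabelled cause-specific quantities, and a ratio above 1 is read as benefit without reference to mortality

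*SAP*

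**What the plan says.** SAP 7.4 analyses time from randomization to the first WHO score of 1 or 2, using Kaplan-Meier curves, a Cox model and a stratified log-rank test. Three of its rules matter here.

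- Deaths: "Participants who die for any reason during the study will be right-censored at Day 60 or date of death, whichever is earlier". For any death before Day 60, this means the date of death.
- Survivors still in hospital: "Participants who complete follow-up without hospital discharge will be censored at the day of their Day 60 visit".
- Missing WHO scores are taken to be above 2, that is, not discharged.

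It then reads the Cox estimate this way: "A hospital discharge rate ratio > 1 indicates a benefit for ANA001". Section 7.4 plans no cumulative-incidence analysis and no sensitivity analysis for deaths. SAP 10.1 only refers back to it.

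Deaths are reported elsewhere. Protocol Table 2 names them among the primary safety parameters of Part 1. SAP 4.3 lists "adverse events leading to study treatment discontinuation and adverse events leading to death", and SAP 7.6.1 plans a table of "All adverse events leading to death". These summaries use the Safety Set and treatment-emergent events, defined in SAP 6: "A Treatment-Emergent Adverse Event (TEAE) is any adverse event that occurs on or after first dosing and up through Day 28".

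**The concern.** On the WHO scale in Protocol Appendix 1, death is score 8 and discharge is score 1 or 2. A death in hospital is therefore a known failure to reach the endpoint, but 7.4 handles it like loss to follow-up. Within the same paragraph, an unknown score keeps a participant at risk as not discharged, while a known score of 8 removes the participant.

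Three consequences follow.

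1. The Kaplan-Meier median comes earlier than the time by which half the arm has actually been discharged.
2. If more participants die on ANA001 and those deaths fall on slow recoverers, the arm is left with an easier-to-discharge risk set. The ratio can then exceed 1 with no effect on discharge speed.
3. If mortality rises but deaths are unrelated to recovery speed, the ratio stays at 1.00 although fewer participants go home. The analysis cannot register that loss.

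Part 1 efficacy may matter beyond description. Protocol 4.1 says that if "no potential for benefit is seen when compared with the placebo group, the DMC may recommend that the study be terminated", and Protocol 6.6.2 lets the sponsor "Modify the sample size and/or endpoints of Study Part 2 if Study Part 1 efficacy data suggests that such changes may be necessary". The same endpoint is primary in Part 2, where Protocol 9.3.4 gives no rule for deaths.

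**Working it through.** **Inputs.** 30 participants per arm and a placebo median of 15 days (Protocol 9.1). Follow-up to Day 60 (SAP 7.4). The documents give no mortality rate, so 5%, 10% and 20% by Day 60 are assumptions.

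**The plan's own figure.** None is given for Part 1. For the same endpoint in Part 2, Protocol 9.1.2 gives 374 events for medians of 15 and 11 days, 85% power and two-sided 0.05. Schoenfeld's formula: 4 × (1.960 + 1.036)² / [ln(15/11)]² = 373.3, rounded up to 374. It reproduces.

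**Median.** Take constant, independent hazards with discharge hazard λ = ln 2 / 15 = 0.0462 per day.

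- Solve μ/(λ+μ) × [1 − exp(−60(λ+μ))] = mortality for the death hazard μ. Results: 0.00258, 0.00541 and 0.01201 per day at 5%, 10% and 20%.
- Then solve λ/(λ+μ) × [1 − exp(−(λ+μ)t)] = 0.5 for the day t by which half the arm is discharged.

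| Mortality by Day 60 | Kaplan-Meier median, deaths censored | Half the arm discharged | Kaplan-Meier discharged by Day 60 | Actually discharged by Day 60 |
|---|---|---|---|---|
| 5% | 15.0 d | 15.4 d | 93.8% | 89.6% |
| 10% | 15.0 d | 15.8 d | 93.8% | 85.5% |
| 20% | 15.0 d | 17.1 d | 93.8% | 77.0% |

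Standard error of a median at 30 per arm: √(0.25/30) / (0.5 × ln 2 / 15) = 3.95 days. The shifts at 5% and 10% are 0.38/3.95 = 0.1 and 0.84/3.95 = 0.2 standard errors.

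**Ratio.** Simulation of 20,000 trials per scenario, 30 per arm, no effect on discharge speed. Discharge is exponential with median 15 days in both arms. Potential death times are uniform on Days 3 to 20 and count only if before discharge, calibrated to the stated mortality. Ratios are geometric means of the unadjusted Cox estimate. The last column is the share of trials with log-rank z > 1.96 favouring ANA001 under the SAP rule (nominal 2.5%).

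Mortality 10% placebo, 20% ANA001:

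| Who dies | SAP rule | Deaths held to Day 60 | z > 1.96, SAP rule |
|---|---|---|---|
| Only the slowest 30% | 1.15 | 0.89 | 6.9% |
| Only the slowest 40% | 1.07 | 0.86 | 4.5% |
| Only the slowest 50% | 1.03 | 0.85 | 3.4% |
| Slowest 30% at three times the risk | 1.06 | 0.85 | 4.2% |
| Unrelated to recovery speed | 1.00 | 0.83 | 2.9% |

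- At 5% versus 10%, the SAP-rule ratios in the same order are 1.05, 1.03, 1.02, 1.03 and 1.00, with z > 1.96 in 4.0% down to 2.7% of trials.
- At 10% in both arms the ratio is 1.00 in every case (2.6% to 2.8%).
- With one extra expected death (10% versus 13.3%), the ratios are 1.04 (slowest 30%), 1.01 (slowest 50%) and 1.02 (three-times risk).
- At 10% versus 20%, the SAP-rule estimate exceeds 1 in 67% of trials (slowest 30%) or 54% (slowest 50%). With deaths held to Day 60 the shares are 34% and 29%. About 50% is expected when neither discharge speed nor mortality differs.
- Stratifying on a baseline severity factor changes little: 1.14 for the slowest 30% and about 1.03 for the slowest 50%.
- A different model, with 30% frail slow recoverers, gives 1.11 under the SAP rule and 0.93 with deaths held to Day 60 at 10% versus 20%.

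**The case against.** A Cox ratio with deaths censored is a valid cause-specific ratio. The benefit sentence can be read as saying only which side of 1 favours ANA001. Protocol 9.3 plans no formal inference in Part 1. Distortion needs unequal mortality concentrated in slow recoverers, and Protocol 5.4 excludes critical illness and patients not expected to survive 48 hours. Holding deaths to Day 60 is a choice of estimand: with no effect on discharge speed it gives 0.83 to 0.89 at 10% versus 20%, because it mixes mortality into the ratio.

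Most of this stands, and it limits the point. It does not remove the missing label, the median that treats the dead as dischargeable, or a benefit sentence that makes no reference to deaths.

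A reader might go further in three ways that the documents do not support.

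- *That mortality goes unreported.* It does not: deaths are a named primary parameter of Part 1. The gap is narrower. The fatal-event table covers treatment-emergent events through Day 28 in the Safety Set, so a death from an event starting on Days 29 to 60 falls outside it, unless it appears among the withdrawal reasons in SAP 7.1. The tables and listings are in a separate document that was not supplied, so a Day 60 display cannot be ruled out.
- *That this ratio drives the futility advice.* The DMC charter and DMC SAP were not supplied, and Protocol 6.6.2 leaves the DMC free to use its own criteria.
- *That a ratio above 1 should never count as benefit when deaths are numerically higher on ANA001.* At 30 per arm with equal true mortality, ANA001 has more deaths by chance in 38% of trials at 5% mortality, 41% at 10% and 44% at 20%. Such a clause would be triggered by noise.

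**Conclusion.** The point holds, with limited scope. Under SAP 7.4 a death before discharge leaves the risk set at the date of death, so the curve and median overstate discharge and the ratio and test are cause-specific without saying so. The effect on the median is small at 5% to 10% mortality. The ratio is sound if mortality is equal or deaths are unrelated to recovery speed. It is pushed above 1 only if more participants die on ANA001 and the deaths fall on slow recoverers: about 1.03 to 1.15 at 10% versus 20%, where 1.15 requires every death to be in the slowest 30%. In the unrelated case it stays at 1.00 while discharge by Day 60 falls from 85.5% to 77.0% (constant-hazard calculation). All of these sizes rest on assumed mortality and the assumed exponential discharge times. The setting is a secondary endpoint of a 60-participant part whose primary endpoint is safety. Protocol 9.3.4's silence on deaths in Part 2 is a detail still to be written, since the supplied SAP covers Part 1 only.

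**What to change.** In SAP 7.4:

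1. Treat participants who die before discharge as not discharged and censor them at Day 60 whatever the date of death, for the curve, median, stratified log-rank test and Cox model. State that a participant discharged before death keeps the discharge event.
2. Keep death-date censoring as a sensitivity analysis, labelled cause-specific.
3. Show all deaths to Day 60 by arm in the Full Analysis Set beside the discharge result.
4. Replace the benefit sentence with: *A ratio > 1 favours ANA001 on hospital discharge and will be interpreted together with deaths to Day 60 by arm.* Add no clause that denies benefit whenever deaths are numerically higher on ANA001.

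Apply the same rule when the Part 2 SAP is written.

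Cost: two sentences, one derivation, one sensitivity table and one row of deaths. Medians become slightly longer (about 0.4 to 0.8 day at 5% to 10% mortality). The main ratio becomes a subdistribution-type measure that mixes mortality with discharge speed, which is why the cause-specific analysis stays beside it.
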